Clinical Trial Protocol

Document Number: c08910926-02		
EudraCT No.:	2016-001236-35	
BI Trial No.:	1368.11	
BI Investigational Product:	BI 655130	
Title:	Multi-centre, open-label, single arm, phase I study to investigate safety, tolerability, pharmacokinetics, pharmacogenomics and efficacy of a single intravenous dose of BI 655130 in patients with active generalized pustular psoriasis.	
Clinical Phase:	I	
Trial Clinical Monitor:		
Phone:	Fax:	
Co-ordinating Investigator:		
Phone:	Fax:	
Status:	Final Protocol (Revised Protocol (based on global amendment 1))	
Version and Date:	Version: 2.0	Date: 09 Nov 2016
Page 1 of 82		
Proprietary confidential information		
© 2016 Boehringer Ingelheim International GmbH or one or more of its affiliated companies. All rights reserved.		
This document may not - in full or in part - be passed on, reproduced, published or otherwise used without prior written permission		

CLINICAL TRIAL PROTOCOL SYNOPSIS

Name of company: Boehringer Ingelheim		Tabulated Trial Protocol		
Name of finished product: Not applicable				
Name of active ingredient: BI 655130				
Protocol date: 22 July 2016	Trial number: 1368.11		Revision date: 09 Nov 2016	
Title of trial: Multi-centre, open-label, single arm, phase I study to investigate safety, tolerability, pharmacokinetics, pharmacogenomics and efficacy of a single intravenous dose of BI 655130 in patients with active generalized pustular psoriasis.				
Co-ordinating Investigator:				
Phone: _____ Fax: _____				
Trial site(s):	Multi-centre trial conducted in 7 countries			
Clinical phase:	I			
Objectives:	To investigate safety, tolerability, pharmacokinetics, pharmacogenomics and efficacy of a single intravenous dose of BI 655130 in patients with active generalized pustular psoriasis.			
Methodology:	Multi-centre, open-label, single arm, single dose			
No. of subjects:				
total entered:	Up to 10			
each treatment:	Up to 10 (single arm study)			
Diagnosis:	Active Generalized Pustular Psoriasis (active GPP)			
Main criteria for inclusion:	
Main criteria for inclusion:
 
• Male or female patients, aged 18 to 75 years at screening (V2)• A known and documented history of Generalized Pustular Psoriasis regardless of the IL36RN mutation status, with previous evidence of fever, and/or asthenia, and/or myalgia, and/or elevated C-reactive protein, and/or leucocytosis with peripheral blood neutrophilia (above ULN)• Presenting with a flare of GPP with at least 10% BSA with			

Proprietary confidential information © 2016 Boehringer Ingelheim International GmbH or one or more of its affiliated companies

Name of company: Boehringer Ingelheim		Tabulated Trial Protocol		
Name of finished product: Not applicable				
Name of active ingredient: BI 655130				
Protocol date: 22 July 2016	Trial number: 1368.11		Revision date: 09 Nov 2016	

erythema and pustules
 
• A GPPGA score of at least moderate severity• GPP patients receiving maintenance treatment with retinoids and/or methotrexate for at least 4 weeks or GPP patients not receiving any maintenance therapy at screening visit 2 (V2)• Male and female patients must agree to use an effective birth control method 
Main exclusion criteria:
 
• Immediate life-threatening GPP flare or requiring intensive care treatment, according to the investigator's judgement. Life-threatening complications mainly include, but are not limited to, cardiovascular/cytokine driven shock, pulmonary distress.• Identified, ongoing serious/severe infection• Acute generalized exanthematous pustulosis (AGEP)• Patient's clinical presentation being considered due to the differential diagnosis of toxic epidermal necrolysis or Stevens-Johnson syndrome• Use of restricted medication (see Table 4.2.2.1:1)• Patients with dose escalation of their maintenance therapy with methotrexate and/or retinoids within the 4 weeks preceding V2 (second screening visit)• Background therapy with ciclosporin within the last 30 days preceding the second screening visit (V2)• Severe, progressive, or uncontrolled renal, hepatic, haematological, endocrine, pulmonary, cardiac, neurologic, cerebral, or psychiatric disease, or signs and symptoms thereof, as judged by the				

Proprietary confidential information © 2016 Boehringer Ingelheim International GmbH or one or more of its affiliated companies

Name of company: Boehringer Ingelheim		Tabulated Trial Protocol			
Name of finished product: Not applicable					
Name of active ingredient: BI 655130					
Protocol date: 22 July 2016	Trial number: 1368.11		Revision date: 09 Nov 2016		
investigator. Patients with less than 3-fold ULN increase in AST and/or ALT and/or alkaline phosphatase and/or with less than 2-fold ULN increase in total bilirubin on infusion day (V3) may be included, provided that no other cause of liver damage than GPP has been identified					
Test product: dose: mode of admin.:	BI 655130 solution for infusion 10 mg/kg Intravenous				
Comparator product: Not applicable					
Duration of treatment: Single dose					
Primary endpoint: The primary endpoint to assess safety and tolerability of BI 655130 administered intravenously, is the number [(N (%))] of patients with adverse reactions, defined as drug-related AEs.					
Secondary endpoints: 
• Percent change from baseline in GPPASI total score at Week 2• Proportion of patients with GPPGA total score of 0 (clear) or 1 (almost clear) at Week 2• Change from baseline in FACIT-Fatigue scale score at Week 2• Change from baseline in Pain VAS score at Week 2					
The following pharmacokinetic parameters will be determined as secondary endpoints: C_{max} , $AUC_{0-\infty}$					

Proprietary confidential information © 2016 Boehringer Ingelheim International GmbH or one or more of its affiliated companies

Name of company: Boehringer Ingelheim		Tabulated Trial Protocol			
Name of finished product: Not applicable					
Name of active ingredient: BI 655130					
Protocol date: 22 July 2016	Trial number: 1368.11		Revision date: 09 Nov 2016		
Further endpoints and parameters of interest:					
Criteria for safety: AEs and SAEs, safety laboratory tests, 12-lead electrocardiogram (ECG), vital signs (blood pressure [BP], pulse rate [PR], body temperature, body weight), injection site reactions, immunogenicity (ADA)					
Statistical methods: Descriptive statistics for safety, PK, and efficacy endpoints					

Proprietary confidential information © 2016 Boehringer Ingelheim International GmbH or one or more of its affiliated companies

FLOW CHART

Trial periods	Screening		Treatment	Observation											End of Trial (EOT)	
				1	1					2	3	4	8	12	16	
Week			1		1					2	3	4	8	12	16	20
Visit	1 ¹	2	3 ^{2,11}	4	5	6	7	8	9	10	11	12	12pc ³	13	13pc ³	14
Days from the day of treatment		Day-1	Day 1	D2	D3	D4	D5	D6	D7	D14	D21	D28	D56	D84	D112	D140
Time window for visits										±1d	±2d	±2d	±2d	±7d	±7d	+7d
Informed consent	X															
Patient's confirmation of participation ⁴		X ⁴														
Infection screening ⁵	X															
IL36RN mutation status ⁶	X															
Demographics	X															
Medical history	X	X														
Alcohol and smoking history	X	X														
Physical examination ⁷	X	X	X	X	X	X	X	X	X	X	X	X		X		X
Vital signs ⁷	X	X	X	X	X	X	X	X	X	X	X	X		X		X
Urine pregnancy test ⁸		X											X	X	X	X
12 lead-ECG ⁹		X		X	X	X				X		X				X
Safety laboratory tests ¹⁰		X	X	X		X				X	X	X				
Review of in-/exclusion criteria	X	X	X													
PK Sampling ¹²			X	X	X	X	X	X	X	X	X	X		X		X
Photographs of skin lesions ¹³			X	X	X				X	X	X	X		X		X
Skin biopsies ¹⁴			X						X	X ¹⁴						
GPPGA and GPPASI			X	X	X	X	X	X	X	X	X	X		X		X

Proprietary confidential information © 2016 Boehringer Ingelheim International GmbH or one or more of its affiliated companies

Trial periods	Screening		Treatment	Observation												End of Trial (EOT)	
				1	1						2	3	4	8	12	16	
Week	1 ¹	2	3 ^{2,11}	4	5	6	7	8	9	10	11	12	12pc ³	13	13pc ³	14	20
Visit	1 ¹	2	3 ^{2,11}	4	5	6	7	8	9	10	11	12	12pc ³	13	13pc ³	14	20
Days from the day of treatment		Day-1	Day 1	D2	D3	D4	D5	D6	D7	D14	D21	D28	D56	D84	D112	D140	
FACIT-fatigue, pain VAS, and PSS			X							X	X		X				
CGI-I										X	X		X				
Presence of edema (yes/no)			X							X	X		X				X
Pustular BSA			X							X	X		X				X
IRT call	X	X	X														X ¹⁶
Dispense/administration study drug ¹⁷			X														
Compliance check			X														
Local tolerability			X	X													
Adverse events ¹⁸	X	X	X	X	X	X	X	X	X	X	X	X		X			X
Concomitant therapy ¹⁸	X	X	X	X	X	X	X	X	X	X	X	X		X			X
Completion of patient participation ¹⁹																	X
Vital status collection														X			X ²⁰

¹ The first screening visit can be performed on any day following the study and trial site initiation

² Visit 3 (infusion day) should be performed the day after Visit 2 (day of admission for the flare)

³ Visits 12pc and 13pc are phone calls and will only be performed by women of childbearing potential: the patient will inform the site team of the result of the urinary pregnancy test. The result will not be recorded in the eCRF but only in the patient's file

⁴ Informed consent will be signed at the first screening visit. As several weeks may elapse until the occurrence of a flare (qualifying event), the patient will be asked to confirm his/her consent to participate in the trial at the second screening visit when he/she is admitted for a GPP flare

⁵ Infection screening will include tuberculosis, hepatitis B, hepatitis C and HIV testing

⁶ IL36RN mutation status from historical patient's data

⁷ Physical examination will include vital signs assessment (BP, PR, body weight and temperature) and general appearance as well as evaluation of all relevant organ systems

⁸ For all female patients of childbearing potential. In case the urine pregnancy test at Visit 2 (Day -1) is positive, it should be repeated for confirmation.

⁹ ECG measurements should always precede blood sampling. Triple ECG will be performed at second Screening Visit (V2) and will be considered as baseline. Single ECG will be recorded at other time points.

¹⁰ Safety laboratory tests include clinical chemistry, haematology, coagulation, and urinalysis, and will be performed locally. On Day 1, the results of the laboratory tests, except tryptase, must be available before the study drug administration.

Proprietary confidential information © 2016 Boehringer Ingelheim International GmbH or one or more of its affiliated companies

11 On Day 1, all baseline blood (plasma, serum, whole blood) and skin biopsy samplings must be performed before trial drug administration. As well, photographs of skin lesions and measurements of GPPGA, GPPASI, FACIT-Fatigue scale, pain VAS, PSS, pustular BSA scores and presence of edema must also be performed before trial drug administration.

12 Please refer to [PK Flow Chart](#) on next page for details.

13 Photographs of skin lesions should always precede skin biopsies and study drug administration

14 Baseline skin biopsies on Day 1: two lesional and two non-lesional skin biopsies of 3 mm punch each, for IHC and RNASeq, should be collected prior to receiving treatment; On Day 7: two lesional skin biopsies of 3 mm punch each should be collected; On Day 14 (optional): two lesional skin biopsies of 3 mm punch each would be collected. See sections [5.6.1](#) and [5.6.3](#)

15 DNA banking is optional and will only be performed in patients who give their consent

16 EOT IRT call must also be performed in case of premature withdrawal

17 Start- and end-time of infusion will be recorded in the CRF.

Proprietary confidential information © 2016 Boehringer Ingelheim International GmbH or one or more of its affiliated companies

GPPASI	Generalized Pustular Psoriasis Area and Severity Index
GPPGA	Generalized Pustular Psoriasis Physician Global Assessment
HBV	Hepatitis B Virus
HCV	Hepatitis C Virus
HIV	Human Immunodeficiency Virus
HPLC-MS/MS	High performance liquid chromatography with tandem mass spectrometry
IB	Investigator's brochure
IEC	Independent Ethics Committee
IHC	Immunohistochemistry
IL	Interleukin
INR	International normalized ratio
IRB	Institutional Review Board
IRT	Interactive Response Technology
ISF	Investigator site file
ITE	Indirect target engagement
IV	Intravenous
λ_z	Terminal rate constant of the analyte in plasma
LDH	Lactate dehydrogenase
LLOQ	Lower limit of quantification
mAb	Monoclonal antibody
MedDRA	Medical Dictionary for Regulatory Activities
MRT	Mean residence time of the analyte in the body after intravenous bolus administration
NOA	Not analysed
NOP	No peak detectable
NOR	No valid result
NOS	No sample available
PD	Pharmacodynamic(s)
PGx	Pharmacogenomics
PK	Pharmacokinetic(s)
PKS	Pharmacokinetic set
PoCC	Proof-of-Clinical-Concept
PR	Pulse rate
PSS	Psoriasis Symptom Scale
QT	Time between start of the Q-wave and the end of the T-wave in an electrocardiogram
QTcF	QT interval corrected for heart rate using the method of Fridericia
RDC	Remote data capture
REP	Residual effect period
SAE	Serious adverse event
SOC	System Organ Class
SRD	Single-rising dose
ss	(at) steady state
SUSAR	Suspected Unexpected Serious Adverse Reaction
$t_{1/2}$	Terminal half-life of the analyte in plasma
t_{\max}	Time from (last) dosing to the maximum measured concentration of the

Proprietary confidential information © 2016 Boehringer Ingelheim International GmbH or one or more of its affiliated companies

	analyte in plasma
TB	Tuberculosis
TDMAP	Trial Data Management and Analysis Plan
TEAE	Treatment-emergent adverse event
TMF	Trial master file
TMM	Team Member Medicine
TNFi	Tumor necrosis factor inhibitor
TSAP	Trial statistical analysis plan
ULN	Upper limit of normal
VAS	Visual Analog Scale
V_{ss}	Apparent volume of distribution at steady state after intravascular administration
V_z	Apparent volume of distribution during the terminal phase after intravascular administration
WOCBP	Woman Of Childbearing Potential

1. INTRODUCTION

1.1 MEDICAL BACKGROUND

Generalized Pustular Psoriasis (GPP) is a life-threatening orphan disease characterized by systemic inflammation affecting the skin and internal organs. It manifests as repeated flares of widespread sterile pustules and diffuse erythema causing significant morbidity and even mortality to GPP patients [[R16-0933](#)]. Systemic symptoms include fever, marked leucocytosis with neutrophilia and elevated serum levels of C-reactive protein. Skin is often painful and tender. Patients are usually uncomfortable, and often febrile.

While GPP flares may be self-limiting (without treatment), the flare duration usually lasts for weeks to months. Over a 2-week period, self-resolution of the flare would not be typically expected (Reference: Expert feedback). In contrast, GPP patients presenting with flares may rather progress to a life-threatening status without treatment. The mean duration of a treated flare is 16 days (range 7-60 days) and mean duration of hospital stay in the acute phase of disease is 10 days (range 3-44 days) [[R16-0933](#)] [[R16-2960](#)]. Complications include sepsis and renal, hepatic, respiratory, and cardiac failure [[R16-0933](#)]. Triggers for GPP flares include infection, corticosteroid use, steroid withdrawal, stress and pregnancy [[R16-0933](#)]. Experts report that the frequency of flares (e.g., annual rate of flares) for an individual patient is unpredictable as well as the pattern i.e., clinical manifestations and rapidity of onset for an individual patient.

Mortality rates up to 7% have been reported but is likely an underestimate [[R16-0933](#)] [[R16-2698](#)] [[R16-1463](#)] due to lack of reported data.

Limited data exist in the literature about treatment of GPP and up to date no gold standard or standard of care is recognized for it. GPP flares are notoriously difficult to treat, and current treatment options for controlling the acute phase of disease are limited and include cyclosporin, retinoids and methotrexate [[R16-0933](#)]. The current treatment options did not show clear efficacy in reducing duration and severity of flares in all patients. Flare recurrences appear to be the norm and occur promptly on withdrawing systemic therapy. Biologics (i.e. TNFi such as Infliximab) have been used and positive case reports have been reported but more robust data on their efficacy is lacking and more information is necessary for conclusions in a non-biased manner and to guide clinical use. Secukinumab (Cosentyx®) and infliximab (Remicade®) have been studied in low patient numbers in Japan and are registered for the treatment of GPP in Japan, but not specifically for the treatment of flares (primary endpoint of the open label studies were at week 16 assessing CGI-Improvement).

The partial response of GPP to currently available agents and their limitations (i.e. safety of cyclosporin and its limitation for long term maintenance treatment) indicate that there is high unmet clinical need for a more effective and tolerated targeted therapy that might overcome current treatment limitations.

IL36R signaling drives skin inflammation in several animal models providing support for the strong link between IL36R biology and skin disorders based on human genetics [[R14-5158](#)].

Proprietary confidential information © 2016 Boehringer Ingelheim International GmbH or one or more of its affiliated companies

Genetic human studies established a strong link between IL36R signaling and skin inflammation, as demonstrated by occurrence of familial generalized pustular psoriasis (GPP) in patients with a loss of function mutation in IL36RN (the naturally occurring receptor antagonist to IL36R) which results in uncontrolled IL36R signaling [[R14-5158](#)]. Deficiency of IL-36Ra has been associated with familial and sporadic GPP. Further genetic linkage between GPP and the IL36 pathway has been recently disclosed. For example, mutations in other genes linked to the IL36 pathway such as CARD14 [[R16-0929](#)] may also lead to GPP.

BI 655130 is a humanized antagonistic monoclonal IgG1 antibody that blocks human IL36R signalling. IL36R is a novel member of the IL1R family. The IL36R is formed as a heterodimeric complex of IL36R and the IL1R accessory protein. The heterodimeric IL36R system with stimulating (IL36 α , IL36 β , IL36 γ) and inhibitory ligands (IL36Ra) shares a number of structural and functional similarities to other members of the IL1/IL1R family, such as IL1, IL18 and IL33. All IL1 family members (IL1 α , IL1 β , IL18, IL36 α , IL36 β , IL36 γ , and IL38) signal through a unique, cognate receptor protein which, upon ligand binding, recruits the common IL1RacP subunit and activates NF κ B and MAP kinase pathways in receptor-positive cell types, leading to enhanced production of downstream inflammatory cytokines/chemokines among which include IL8, IL6, and TNF α . BI 655130 could provide benefit as targeted therapy to GPP patients presenting with a flare of GPP by blocking the IL36 pathway and potentially reducing the severity and duration of disease-related symptoms.

Of note, it has been shown recently in children from families who had neonatal onset of sterile multifocal osteomyelitis, periostitis, and pustulosis that the absence of interleukin-1 receptor antagonist allows unopposed action of interleukin-1, resulting in life-threatening systemic inflammation with skin and bone involvement which responded to empirical treatment with the recombinant interleukin-1-receptor antagonist anakinra [[P09-07583](#)]. Strikingly, the patients showed an early response to targeted treatment of Anakinra with pustulosis resolving after days and even bone changes after only weeks. This latter disease model validates the relevance of therapeutic strategies relying on targeted inhibition of a unopposed, pathogenic IL1 family pathway.

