3.2 DISCUSSION OF TRIAL DESIGN, INCLUDING THE CHOICE OF CONTROL GROUP(S)

This phase I trial is the first study with BI 655130 to be conducted in GPP patients.

Current safety data about BI 655130 were obtained from a previous first-in-man phase I trial carried out in healthy volunteers. BI 655130 was safe and well tolerated in all dose groups tested in this trial up to the 10 mg/kg dose.

Non-clinical safety data are limited as BI 655130 could not be directly tested in preclinical toxicity studies (a surrogate antibody specific to mouse was used instead). The main objective of this phase I trial is to investigate safety and tolerability of BI 655130 in patients with a flare of GPP.

Proprietary confidential information © 2016 Boehringer Ingelheim International GmbH or one or more of its affiliated companies

As a phase I trial, endpoints also include pharmacokinetics and pharmacogenomics.

Efficacy is an exploratory endpoint at this early stage of the development. Final data will be compared to baseline.

For the first trial in GPP (1368.11) it is planned to include patients with active disease regardless of the mutation status (while the status will be investigated during the trial) for the following reason:

- In addition to the described IL36RN mutation, other mutations in the same gene and other genes linked to the IL36 pathway (please see [section 1.1](#) “Medical Background” above) have been described pointing to a general role of the IL36 pathway (and not only the IL36RN mutation) as disease trigger/driver
- Patients can be included without need for screening for mutation status (critical as onset of treatment, treatment of acute flares has to be fast)

No active control group is included in this trial as there is currently no drug approved for the induction treatment of flares. Secukinumab (Cosentyx®) and infliximab (Remicade®) are registered for the treatment of GPP in Japan, but not specifically for flares. For secukinumab, authorization was granted on the basis of long-term treatment data (52 weeks) derived from one clinical trial conducted in patients with chronic GPP, not necessarily presenting with a flare episode at the time of inclusion. This study did not specifically evaluate the efficacy of secukinumab during flares (primary endpoint was proportions of patients who achieved treatment success at week 16) [[R16-1462](#)].

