7.4.5 Efficacy

The following rules will be used to impute for missing data:

- For continuous endpoints, and for the CGI-Improvement, under the assumption that the disease is self-limiting and will gradually improve over time, the Last Observation Carried Forward (LOCF) approach is intended to be used;
- For binary endpoints, the following will be performed:

Proprietary confidential information © 2016 Boehringer Ingelheim International GmbH or one or more of its affiliated companies

- o If there are data at visits both before and after the visit with a missing outcome, then impute as success only if both neighboring visits also represent a success;
- o Otherwise, impute as a failure to achieve a response (i.e. NRI [No Response Imputation]).

For patients that take a rescue medication during the course of the study, efficacy outcomes subsequent to the time-point at which the medication was taken will be set to missing and will be imputed using the steps described above.

For continuous endpoints, the data will additionally be displayed in the original form without any imputation for missing data performed.

Details on the handling of missing item scores for the FACIT will be based on FACIT Administration and Scoring Guidelines (version 4) and provided in the TSAP.

Further imputation strategies for missing data will be considered in the TSAP.

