### Binary efficacy endpoints

Some efficacy endpoints are defined in terms of the proportion of patients with a particular binary outcome, i.e. achievement of a GPPGA total score of 0 or 1. For those binary outcomes, the different methods for handling of missing data, presented below, will be performed as presented in Table 6.3: 1. Please note that some of these binary outcomes are derived from other parameters, but imputation is planned to take place only at the binary level, i.e., the GPPGA total score itself will not be imputed, but the binary endpoints derived based on these scores will be imputed.

- The following primary imputation strategy ("NRI") will be performed:
  - If there are data at the visits both immediately before and immediately after the visit with a missing outcome, then impute as success only if both the preceding and the following observations also represent a success (independent of whether the preceding and following observations were selected for analysis based on time windows described in [Section 6.7](#));
  - Otherwise, impute as a failure to achieve a response (i.e. no response imputation [NRI]).

For patients who take a rescue medication (as defined in [Section 5.3.4](#)) during the course of the study, all efficacy outcomes measured after the day of first use of rescue medication will be set to missing and, during the on-treatment period, will be imputed using the steps described above.

- Observed cases (OC) approach will be used as a sensitivity analysis and will include all collected data, with no imputation performed on the missing data. Such an OC approach will exclude all values measured after intake of a rescue medication (i.e. such values will be set to missing).
- Observed cases including rescue (OC-IR) approach will be used as a further sensitivity analysis and is an extension of the OC approach which includes additionally all values which were measured after rescue medication intake.

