#### Continuous efficacy endpoints

For continuous efficacy endpoints, such as the pain VAS, FACIT-Fatigue scale score, and GPPASI total score, the different methods for handling of missing data, presented below, will be performed as presented in [Table 6.3: 1](#):

- Imputation technique ("LOCF"): Under the assumption that the disease is self-limiting and will gradually improve over time, the LOCF approach will be used as the primary imputation strategy to replace missing values either at intermediate visits or due to early withdrawal from the trial. The last available value, including baseline, will be carried forward to all subsequent visits within the on-treatment period at which a measurement is missing. Values measured after the day of first rescue medication intake (as defined in [Section 5.3.4](#)) will be set to missing and the missing values within the on-treatment period will be imputed by LOCF.
- In addition, as sensitivity approaches, the OC and OC-IR will also be performed.

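### LOCF is justified by assumed self-improvement that Protocol 1.1 does not support at Week 2, so a patient who dies, or leaves for worsening without an exit assessment, can keep an improved continuous score

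*Protocol*

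**What the plan says.** **Natural course.** Protocol 1.1 allows that flares may be self-limiting, but over weeks to months. It then says: "Over a 2-week period, self-resolution of the flare would not be typically expected". It adds that "GPP patients presenting with flares may rather progress to a life-threatening status without treatment".

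**Imputation premise.** Protocol 7.4.5 adopts LOCF for continuous endpoints "under the assumption that the disease is self-limiting and will gradually improve over time". SAP 6.6.2 repeats this premise and makes LOCF the primary imputation.

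**Imputation rule.** SAP 6.6.2 uses LOCF to "replace missing values either at intermediate visits or due to early withdrawal from the trial", and states: "The last available value, including baseline, will be carried forward to all subsequent visits within the on-treatment period at which a measurement is missing". The visible text has no separate rule for death or deterioration.

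**Binary endpoint.** For GPPGA 0/1, a missing visit counts as a success only if the observations on both sides are successes. "Otherwise, impute as a failure to achieve a response" covers every other case.

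**Sensitivity analyses.** For continuous endpoints these are observed cases without (OC) and with (OC-IR) values after rescue.

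**Reading of efficacy.** There is no control group. Protocol 3.2 says: "Final data will be compared to baseline".

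**The concern.** All four secondary efficacy endpoints are read at Week 2, and three are continuous. LOCF is cautious when patients would otherwise go on improving, because it freezes them at an earlier, worse state. That is the role the stated premise gives it. Where a flare can instead progress, LOCF can freeze a patient at a better state than the true one.

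The clearest case is death, because no later value can exist. A patient whose Day 7 score was improved and who then dies enters the Week 2 mean as an improver, while the binary endpoint counts the same patient as a failure. With 6 to 10 patients, one such case visibly moves the mean. Protocol 2.1 and 2.2 intend the results to establish proof of clinical concept and to support discussions with health authorities, so the estimates themselves are what the trial delivers.

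**Working it through.** The plan states no figure to reproduce: the sample size rests on feasibility and all analyses are descriptive. The check traces the rules and then sizes one affected patient.

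**1. Death without prior rescue, after Day 7 and before a Week 2 value is obtained.**
- Protocol 5.1.2 schedules GPPASI at Visits 3 to 10, with nothing between Day 7 and Day 14. FACIT-Fatigue and pain VAS are taken on Days 1, 7, 14 and 28.
- No exit examination is possible, so the last value stands.
- SAP Table 6.1:1 runs the on-treatment period to Day 140 after infusion. GPPASI is therefore carried to Weeks 2, 4 and 12. FACIT-Fatigue and pain VAS are carried to Weeks 2 and 4, since they are not collected later and SAP 6.7 displays only planned visits.
- GPPGA 0/1 has no following observation, so it is a failure.
- OC and OC-IR have no later value, so the patient leaves the mean.

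**2. Withdrawal for worsening or lack of efficacy.**
- Protocol 3.3.4.1 and 6.2.3 require complete V12 procedures at discontinuation, which include GPPASI, FACIT-Fatigue and pain VAS. After V12, the end-of-trial procedures apply instead.
- SAP 6.7 imputes from every available observation, selected in a window or not. A worsened exit value therefore replaces the Day 7 value, and on Days 11-17 it falls in the Week 2 window itself.
- An earlier improvement survives only if that examination is missed or cannot be completed. Protocol 6.2 says questionnaires the patient cannot complete unaided are left blank, which affects FACIT-Fatigue and pain VAS only.

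**3. Size for one patient.** The proposed rule scores an improved last value as baseline, that is 0% reduction. If the carried reduction is r% among n patients, the shift in the mean is r/n. The values r = 50 and 80 are assumed; n = 6 and 10 are the protocol's limits.

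| n | r = 50 | r = 80 |
|---|---|---|
| 6 | 50/6 = 8.3 points | 80/6 = 13.3 points |
| 10 | 50/10 = 5.0 points | 80/10 = 8.0 points |

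**4. Effect on the planned interval.** Take n = 8 and assume the other 7 patients have mean 60 and SD 25. The SAP 7.5.2.1 t-interval, mean ± t × SD/√n, gives:
- carried 50%: mean (7×60 + 50)/8 = 58.8, 95% CI 39.2 to 78.3;
- scored 0%: mean (7×60 + 0)/8 = 52.5, 95% CI 26.3 to 78.7;
- OC, patient dropped: mean 60.0, 95% CI 36.9 to 83.1.

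OC gives the highest mean of the three, so it does not reveal the problem.

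**5. Frequency.** Protocol 1.1 says "Mortality rates up to 7% have been reported but is likely an underestimate" and gives no time base, so no 2-week risk can be derived. Exclusion criterion 2 removes immediately life-threatening flares, which lowers the early risk.

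**The case against.** The best defence has four parts.

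- **The two statements can coexist.** A flare may improve gradually and still not resolve within 2 weeks. This is fair: a reader might infer that the plan contradicts itself outright, or that change from baseline is therefore uninterpretable, and the documents do not go that far. Protocol 3.2 justifies the lack of a control by the absence of an approved drug and by feasibility, not by Section 1.1. What remains is that possible progression removes the ground for presuming LOCF conservative at Week 2.
- **Exit examinations close most of the withdrawal route.** This stands. A reader might infer that anyone leaving for an adverse event or worsening keeps an earlier improvement; the exit rule and SAP 6.7 prevent that whenever the examination is done. Overriding an improved value actually observed at exit after an adverse event would be a choice of estimand, not the correction of an error. Patients who worsen may also receive rescue and stay in follow-up, and OC-IR retains their later values.
- **The event is rare.** A reader might apply 7% per patient and obtain 1 - 0.93^6 = 35% to 1 - 0.93^10 = 52% for at least one death. That does not fit a Week 2 endpoint: the 7% is an undated upper figure, and deaths after the Week 2 visit cannot move the Week 2 mean.
- **Other displays would expose it.** Unimputed data, individual listings and disposition are planned, as is a GPPASI median with a confidence interval. These help a careful reader, but no visible continuous analysis scores the event as unfavourable.

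Two further limits apply. LOCF keeps the last value, not the best. FACIT-Fatigue and pain VAS also have no scheduled post-baseline value before Day 7, so an earlier death carries baseline. SAP 5.3.4 and 9.1 are absent from the public text, so a death rule there cannot be excluded, although 6.6.2 cites them only for the rescue definition and score derivation.

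**Conclusion.** The point holds in a narrow form. The stated premise does not support LOCF as conservative at Week 2. The rule lets an improved value stand after death without prior rescue, and after withdrawal for worsening or lack of efficacy when the endpoint was not assessed at exit. It does not hold for withdrawals with a completed exit examination.

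When the event occurs, it shifts the Week 2 GPPASI mean by 5-8 points at n=10 or 8-13 points at n=6, assuming a carried reduction of 50-80% compared with 0%. If the last value was no better than baseline, there is no such inflation. The probability cannot be derived from the documents and is probably low. Because the analysis is descriptive, the effect is on estimates and intervals, not on an error rate.

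**What to change.** - In Protocol 7.4.5 and SAP 6.6.2, delete the self-limiting justification for LOCF.
- In SAP 6.6.2, add a rule for continuous endpoints. For visits missing after death, or after discontinuation for worsening or lack of efficacy with no exit assessment of that endpoint, impute the worse of the baseline and last observed values (higher for GPPASI and pain VAS, lower for FACIT-Fatigue).
- Keep LOCF, including observed exit values, for all other gaps.
- Report full LOCF as a sensitivity analysis.

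The cost is one SAP paragraph and a flag built from the discontinuation reason, which the CRF already records. No new data are needed. The downside is slightly less favourable means if such an event occurs.
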